6.1.2.8 Proportion of children cured at Day 7 follow-up

A child is defined as cured if he/she recovers from illness. A child will be counted in the numerator as cured if his/her status at the time of Day 7 follow-up is at home “well, completely recovered” and the follow-up date is within 7 days of Day 0, considering a + 3 days window (10th day included). The denominator will be all children recruited.

Children for whom no Day7 data are available or withdrew prematurely from the study will be assumed cured by Day7.

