Quantitative research assistants will conduct the phone follow-up interviews using an EDC mobile application. Personally identifiable information (PII) will be used for contacting caregivers. No time window applies to Day 7 follow-up. A window of +7 days applies to Day 28 phone call attempts (Day 28 to Day 35).

Data that will be collected at Day 7 follow-up will include cure status (recovery from illness as reported by the caregiver), death and hospitalization information between Day 0 and Day 7 as

reported by caregivers. The primary outcomes on the proportion of children with severe complications by Day 7 and on the proportion of children admitted to hospital within 24 hours of the Day 0 primary care consultation as a result of a referral will be assessed based on Day 7 follow-up. Hospital name, duration of hospitalization and reason for admission will be collected for children reported to have been hospitalized to facilitate the retrospective data collection at referral hospital level.

Data collected at Day 28 follow-up will include death and hospitalization information as reported by the caregiver. The secondary outcome on the proportion of children with severe complications at Day 28 will be assessed on the basis of this interview.

Higher level of care visit

Data collection will be conducted retrospectively at all government-designated and private referral facilities within the study area, including hospitals or emergency / inpatient area of larger primary or secondary care facilities (e.g., study facilities that can admit paediatric patients). A quantitative research assistant using the EDC mobile application will collect data from referral facility records, registries and discharge summaries to document hospitalization for all children reported to have been hospitalized between Day 0 and Day 7. Personally identifiable information will be collected to cross-check the identity of the patients. Arrival date and time, basic clinical information on arrival and, if admitted, admission and discharge diagnosis, and admission duration and outcome will be collected. If available, data on oxygen saturation at admission, oxygen administration and intensive care unit (ICU) admission and duration will also be recorded.

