6.1.1 General definitions

Day 7 / Day 28 assessment

Day 7 / Day 28 assessment refers to information reported by the caregiver after Day 0 and recorded in Day 7 / Day 28 forms. Data collected as part of unscheduled visits are also integrated in these forms.

If multiple successful follow-up assessments for the same child are recorded within Day7 or Day28 databases, the most recent follow-up assessment within each database will be used. To limit potential recall bias, assessments conducted far beyond the expected follow-up time will be dropped. This will be 30 and 60 days from Day 0 for Day 7 and Day 28 respectively.

Death

A child will be considered deceased if, from Day 7 / Day 28 assessment, his/her status at the time of follow-up is “deceased”. In case of implausible death date (i.e. prior to enrolment date), death will be handled as follow:

- ξ if death date is recorded at Day7 follow-up, death will be assumed to be within 7 days of Day0
- ξ if death date is not recorded at Day7 follow-up but only at Day28 follow-up, death will be assumed to be after 7 days of Day0 but within 28 days.

Hospitalisation

A child will be considered hospitalised if, from Day 7 / Day 28 assessment, he/she went to a hospital, was admitted overnight or if his/her status at the time of follow-up is “hospitalised”. In case of implausible hospitalisation date (i.e. prior to enrolment date), hospitalisation will be handled as follow:

- ξ if hospitalisation date is recorded at Day7 follow-up, hospitalisation will be assumed to be within 7 days but after 24hrs of Day0
- ξ if hospitalisation date is not recorded at Day7 follow-up but only at Day28 follow-up, hospitalisation will be assumed to be after 7 days of Day0 but within 28 days.

Hospitalisation within 24hrs of Day0

For the purpose of primary analysis, a child will be considered admitted to hospital 24hrs of Day0 consultation if the date of hospitalisation is the same as Day0 date or is one day after Day0 date.

Referral

A child will be considered to be referred (either to a hospital or to an inpatient part of a larger primary healthcare facility) if, at Day0, the caregiver confirms that the child was urgently referred or the research assistant confirms that an urgent referral advice was recorded for the child. If urgency is unknown from both sources, referral will be assumed to be urgent.¹

Antibiotics

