6.1.2 Health, hospitalisation and referral outcomes

6.1.2.1 Proportion of children with a severe complication by Day 7

Severe complication is defined as death or secondary hospitalisation. Secondary hospitalisation refers to any delayed hospitalisation (occurring at any point greater than 24hrs after the Day 0 consultation) and any hospitalisation occurring without a referral.

Information on death and hospitalisation will be taken, in order, from:

- ξ Day7 follow-up assessment
- ξ If Day7 follow-up assessment is missing, Day28 follow-up assessment

Death will be counted in the numerator if death date is within 7 days of Day0 (7th day included). Hospitalisation will be counted in the numerator if the child was not referred at Day0 or hospital admission date is within 7 days of Day0 (7th day included) but after 24hrs of Day0.

The denominator will be all children recruited. Children for whom no death and hospitalisation data are available or withdrew prematurely from the study will be assumed to be alive and not hospitalised by Day7.

6.1.2.2 Proportion of children with a severe complication by Day 28

Severe complication is defined as per the outcome above.

Information on death and hospitalisation will be taken, in order, from:

- ξ Day7 follow-up assessment
- ξ If Day7 follow-up assessment is missing or no outcomes were reported, Day28 follow-up assessment
- ξ If both Day7 and Day28 assessments are missing or no outcomes were reported, unscheduled visits (deaths only)

Death will be counted in the numerator if death date is within 28 days of Day0 (28th day included). Hospitalisation will be counted in the numerator if the child was not referred at Day0 or hospital admission date is within 28 days of Day0 (28th day included) but after 24hrs of Day0.

The denominator will be all children recruited. Children for whom no death and hospitalisation data are available or withdrew prematurely from the study will be assumed to be alive and not hospitalised by Day28.

6.1.2.3 Proportion of children admitted to hospital within 24 hours of Day 0 consultation and as a result of a referral

Information on hospitalisation will be taken, in order, from:

- ξ Day7 follow-up assessment
- ξ If Day7 follow-up assessment is missing, Day28 follow-up assessment

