6.1.2.6 Proportion of children who completed referral as reported at Day 7 follow-up

A referral will be considered completed if a child attended a hospital, whether he/she was admitted or not. Children will be counted in the numerator if they received a referral advice (as per definition above) and their caregiver reported to have sought care in a hospital and

the follow-up date is within 7 days of Day 0, considering a + 3 days window (10th day included). The denominator will be all children recruited.

Additionally, the proportion will be calculated and reported using only children who were referred as denominator.

Children for whom no Day7 data are available or withdrew prematurely from the study will be assumed not attending a hospital by Day7.

6.1.2.7 Proportion of children with non-severe disease referred to a higher level of care on Day 0

Children with non-severe disease who received a referral advice (as per definition above) at Day0 will be counted in the numerator. The denominator will be all children recruited. Non-severe disease will be defined in a separate document.

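### Day-7 cure (secondary outcome): a recovered child reached on Days 11 to 30 is scored not cured, while a child never reached, or dead by Day 7 on the Day-28 form alone, is scored cured

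*SAP*

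**What the plan says.** SAP 6.1.2.8 counts a child as cured when the caregiver reports full recovery at home and the follow-up date falls within seven days of Day 0, "considering a + 3 days window (10th day included". The denominator is all recruited children. For the rest, "Children for whom no Day7 data are available or withdrew prematurely from the study will be assumed cured by Day7".

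Three other rules decide who has Day-7 data:

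- Protocol 8.1.1: "No time window applies to Day 7 follow-up". SAP 3.8 repeats this.
- SAP 6.1.1 drops assessments made long after the planned day and sets the limits: "This will be 30 and 60 days from Day 0 for Day 7 and Day 28 respectively". A Day-7 form completed on Days 11 to 30 is therefore kept.
- SAP 6.1.1 defines a Day-7 or Day-28 assessment by the form in which the information was recorded.

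Two neighbouring outcomes handle the same situations differently. Completed referral (SAP 6.1.2.6) uses the same Day-10 limit, but there "Children for whom no Day7 data are available or withdrew prematurely from the study will be assumed not attending a hospital by Day7". Severe complication by Day 7 (SAP 6.1.2.1) has a second source, "If Day7 follow-up assessment is missing, Day28 follow-up assessment", and works by date: "Death will be counted in the numerator if death date is within 7 days of Day0 (7th day included".

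Protocol 6.4.2 defines cure only as caregiver-reported recovery at the Day-7 follow-up. The Day-10 limit and the assumption for children without data are both SAP additions.

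**The concern.** A child reached on Day 15 and a child never reached have the same problem: nobody recorded their status near Day 7. The SAP scores the first as a failure and the second as a success. The scored cure rate then depends on how hard and how late families were traced as well as on recovery, and an arm that traces more of its hard-to-reach children late lowers its own rate.

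Late contacts are an expected product of the follow-up scheme in Protocol 6.5.1. After a failed first call, further attempts run over the next three days. In-person follow-up, where consented, comes only after the remote attempts have failed. If the first call is on Day 7, the three daily attempts end on Day 10, so the in-person contacts are the most exposed.

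The missing-data analyses in SAP 6.2.4 and 6.3 concern the primary outcomes, so nothing planned would reveal the problem for cure.

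**Working it through.** **Step 1. Apply the rules child by child.**

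| Child | Usable Day-7 data? | Cure (6.1.2.8) |
|---|---|---|
| Recovered, reached by Day 10 | Yes | Cured |
| Not recovered, reached by Day 10 | Yes | Not cured |
| Recovered, reached Days 11 to 30 | Yes, form kept | Not cured, fails the date test |
| Reached only after Day 30 | No, form dropped | Assumed cured |
| Never reached, or withdrawn without data | No | Assumed cured |
| No Day-7 form; Day-28 form dates death by Day 7 | No | Assumed cured |

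The child in the last row is a severe complication under 6.1.2.1. Under 6.1.2.6, a referred child who went to hospital counts as not completed both when reached late and when never reached, so that outcome does not have the mismatch.

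**Step 2. Inputs.** The plan gives no power, sample size, loss or lateness figure for cure, so there is no stated figure to reproduce.

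- R, true cure rate: 0.92, the routine-care figure cited in Protocol 3.2.
- a, share reached by Day 10: 0.90, an assumption borrowed from the pilot criterion of 90% reachable by phone (Protocol 6.4.1).
- b, share reached on Days 11 to 30, and c, share with no usable Day-7 data: assumptions, with a + b + c = 1.

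**Step 3. Scored cure rate.** Reached by Day 10 contributes a × R, late contributes 0, and unreached contributes c:

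scored = a × R + c

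- Arm with b = 0.05, c = 0.05: 0.90 × 0.92 + 0.05 = 0.828 + 0.05 = 87.8%.
- Arm with b = 0.07, c = 0.03: 0.828 + 0.03 = 85.8%.
- Gap with no true effect: 87.8 − 85.8 = 2.0 points.
- Limits for the same 10%: all late, 82.8%; none reached, 82.8 + 10 = 92.8%. These are bounds, not expected arm differences.

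With a and R equal in both arms, the gap equals the difference in c. Each percentage point of children moved from unreached to reached late lowers the scored rate by one point. For scale, Protocol 3.2 cites a 5-point difference (97% against 92%) for an earlier decision tool; 2.0 / 5 = 0.4 of that.

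**Step 4. Early deaths scored as cured.** The Tanzanian arm is 22 × 1,680 = 36,960 children. Assume 0.05% to 0.2% die by Day 7 and 5% to 10% of those deaths are known only from the Day-28 form:

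- Low: 36,960 × 0.0005 × 0.05 = 0.9.
- High: 36,960 × 0.002 × 0.10 = 7.4.

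That is about 1 to 7 children per arm.

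**Step 5. The other reading.** Suppose missing Day-7 data was meant to include forms dated after Day 10. Then scored = a × R + b + c = 0.828 + 0.10 = 92.8% for any split, and the false gap disappears. But children whose caregivers reported on Days 11 to 30 that they had not recovered would be scored cured. The 30-day retention rule in 6.1.1 makes this the weaker reading, and the text would still need correcting.

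**The case against.** Several arguments against the point carry weight.

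- *A recovered child first reached on Day 20 may not have been well on Day 7.* True, and a contact window is defensible. The fault is only the pairing of that window with success for children who have no data.
- *The 2.0-point gap needs unequal late tracing.* Also true. The documents show no difference between arms, and Protocol 7.2 has phone outcome data collected by assistants blinded to arm and facility. The gap is an illustration, not a forecast.
- *Early deaths known only from the Day-28 form are few.* Agreed. That row is a contradiction between two outcomes, not a material bias.
- *Cure does not decide the trial.* SAP 4.1 rests positivity on the primary outcomes.

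Some stronger inferences are not supported:

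- A reader might count dilution of a true effect as a result of the mismatch. With equal contact patterns a 5-point difference does read 0.90 × 5 = 4.5 points, but any rule giving one fixed value to everyone not reached by Day 10 does the same, including the rule in 6.1.2.6.
- A reader might think the SAP leaves open which of two Day-7 records counts. It does not: "the most recent follow-up assessment within each database will be used".
- A reader might call it an error that the second primary ignores hospital records for referred children lost to follow-up, a search that Protocol 6.5.1 and 8.2.4 provide for. Protocol 8.1.1 bases the primaries on the Day-7 follow-up, so the SAP is not in error there.
- A reader might fault the SAP for running imputation and worst-case analyses only above about 10% missing. That trigger is the protocol's own (8.3.1).

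**Conclusion.** SAP 6.1.2.8 is wrong as written and should be corrected. It affects a secondary outcome; neither primary uses the rule. The scoring contradiction follows from the text and needs no assumption about contact rates.

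Its size does need assumptions. With 92% true cure and 90% reached by Day 10 in both arms, a two-point difference in the share never reached gives a false two-point difference in cure. Actual loss and lateness are not given, and with equal contact patterns the mismatch creates no false difference between arms. The documents do not support saying that the cure comparison will be biased, only that it would be if late tracing differed by arm, with no planned check to show it.

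**What to change.** In SAP 6.1.2.8, score children alike whether their Day-7 record is absent, dropped or dated after Day 10. Either form will do, with the other as a sensitivity analysis:

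- treat them all as missing and analyse cure among children of known status; or
- give them all the same value and keep all recruited children as the denominator.

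In both, count any death dated by Day 7, from any source, as not cured.

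**Cost.** SAP wording and a little programming; no new data.

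- The known-status version has a smaller denominator and assumes that children reached by Day 10 are representative.
- It also admits late-reported deaths but not late-reported recoveries. With 10% unreached, and all of a 1.1% complication rate taken as deaths, 0.10 × 0.011 = 0.0011 is added to the denominator, and 0.828 / 0.9011 = 91.9% against 92%. That is about 0.1 point at most.
- The single-value version shrinks a true difference to the share reached by Day 10.

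**Two minor edits on the primaries in the same revision.**

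- SAP 4.3 runs the complete-case analysis unconditionally, including for the DMC. SAP 6.2.4 and 6.3 make it conditional on substantial missing data, and 6.2.4 keeps sensitivity analyses out of DMC reports. These should be reconciled.
- SAP 6.3 should define best and worst case separately for each primary, because not being hospitalised is the unfavourable value for the second.

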6.1.3 Antibiotic-related outcomes

6.1.3.1 Proportion of children prescribed an antibiotic at Day 0

Information on antibiotics prescription are recorded by the RA on Day 0, after the clinical consultation. The data collection tool is structured in a way to facilitate the reporting of antibiotics, starting with single-drug questions for the most common/important ones to drop-down lists for other antibiotics/treatments and free text. All options will contribute to determine whether an antibiotic prescription was given. A child will be considered prescribed with an antibiotic if:

- ξ “Yes” was selected for at least one single-drug question
- ξ “No” was selected for all single-drug questions but one or more antibiotics were selected from the antibiotics/treatments drop-down list
- ξ “No” was selected for all single-drug questions, antibiotics were not selected from the other antibiotics/treatments drop-down list but antibiotics were listed in the free text field (conditional to feasibility of assessing free text)

All children recruited will be counted in the denominator.

6.1.3.2 Proportion of children prescribed a diagnosis-appropriate antibiotic

Appropriateness of antibiotic prescription in relation to diagnosis will be evaluated as:

- ξ Proportion of children who received a diagnosis for which a systemic antibiotic was indicated and a systemic antibiotic was prescribed
- ξ Proportion of children who received a diagnosis for which a systemic antibiotic was not indicated and systemic antibiotic was prescribed

- ξ Proportion of children who received first-line (or second-line) antibiotics according to recommendations for IMCI diagnoses for which specific antibiotic(s) are indicated

Only children with a diagnosis for which a systemic antibiotic was indicated will be counted in the denominator for the first proportion, only children with a diagnosis for which a systemic antibiotic was not indicated will be counted in the denominator of the second proportion, and only children who received an IMCI diagnosis requiring specific antibiotics will be counted in the denominator of the third proportion.

Diagnoses will be classified according to whether systemic antibiotics are indicated, based on IMCI and other relevant national guidelines as used for the CDSA, using the structured data entry and free text if feasible. Diagnosis classification will be defined in a separate document.

6.1.4 Antimalarial-related outcomes

Although the following outcomes need to share the same definition for a cross-country analysis, it is acknowledge that malaria testing strategies are different across countries. In Tanzania all febrile children (≥ 60 days) should be tested for malaria. In India febrile children should be tested only in high risk areas (or seasons), or in low risk areas if there is history of travel to a high risk area or when no other obvious cause of fever is detected. This difference will need be taken into account when reporting these outcomes. Untested febrile children will need to be described more in detail for India.

6.1.4.1 Proportion of febrile children tested for malaria at Day 0

A child will be considered to be febrile if, at Day 0, history of fever was reported by the caregiver before the consultation or temperature was recorded to be above or equal 37.5 C° or fever was recorded elsewhere in the registry (e.g. diagnosis).

A child will be considered tested for malaria if a malaria test was ordered during the consultation and a test result is available (i.e. positive, negative, invalid/indeterminate, reported but handwriting not readable).

Only febrile children will be counted in the denominator.

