admission) and admission outcome (final diagnosis, discharge against medical advice, death). The same data will be collected for children who visit a non-hospital higher-level of care (emergency or admission unit of a primary or secondary care facility).

It is expected that some participants may present at the same or another health facility enrolled in the study during the follow-up period. These visits and the findings will be recorded on the appropriate scheduled / unscheduled visit eCRFs.

[figure not shown]

Fig. 5. Flowchart of the pragmatic cluster randomised controlled trial. CDSA = Clinical Decision Support Algorithm. CG = Caregiver. HCP = Healthcare provider. OPD = Out-patient department. Arm 1 not applicable in India.

Tab. 4. Schedule of the visits and associated CRFs for the pragmatic cluster RCT. Arm 1 not applicable in India. The different types of data collectors are represented by the following icons:

 Facility-based research assistants

 Research assistant rotating between different referral health facilities

 Healthcare providers

 Call centre-based research assistant

		Health facility baseline visit			Higher level of care visit ^{1,Err r!} Bookmark not defined.			Scheduled ² or unscheduled visit at any study facility			Phone follow-up		
		Time point / window	Day 0		Day 0-7	Day 1 -28			Day 7	Day 28 [28 - 35]			
		Data collection method	Prospective data collection		Review of medical records / registries	Prospective data collection			Phone interviews	Phone interviews			
		Randomization ³	Arm I	Arm II	Arm III				Arm I	Arm II	Arm III		
Events		Forms											
Informed consent			-										
Screening			TIMCI-01										
Identification & contact information	Full identification		TIMCI-02a										
	Contact information		TIMCI-02b										
	Identification and contact information check		TIMCI-02c										
	Referral facility identification		TIMCI-02d										
	Follow-up identification check		TIMCI-02e										
Socio-demographics			TIMCI-03										
Visit info		Care seeking behaviour, transport and costs for visiting health facility reported by caregiver	TIMCI-04a										

	Visit and admission info recorded by referral facility (medical records, registries) ^{Error! Bookmark not defined.}	TIMCI-04b											
	Patient journey reported by caregiver at follow-up	TIMCI-04c											
Clinical presentation & medical history	Clinical presentation and medical history reported by caregiver at baseline	TIMCI-05a											

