	Medical history recorded in clinical notes and / or facility registries	TIMCI-05b											
	Chief complaints and medical history recorded in CDSA	TIMCI-05c											
Basic measurements & physical exams	Basic measurements and physical exams recorded in clinical notes and / or facility registries	TIMCI-06a											
	Basic measurements and physical exams recorded in CDSA	TIMCI-06b											
Respiratory rate & pulse oximetry	Respiratory rate and pulse oximetry recorded in clinical notes and/or facility registries ^{Error! Bookmark not defined.}	TIMCI-07a											
	Respiratory rate and pulse oximetry recorded in CDSA ^{Error! Bookmark not defined.}	TIMCI-07b											
	Respiratory rate and oxygen saturation recorded at arrival by referral facility ^{Error! Bookmark not defined.}	TIMCI-07c											
Laboratory investigations	Laboratory investigations recorded in clinical notes	TIMCI-08a											

	and / or facility registries <small>Error! Bookmark not defined.</small>									
	Laboratory investigations recorded in CDSA ¹ <small>Error! Bookmark not defined.</small>	TIMCI-08b								
Diagnosis & care management	Diagnosis and care management in clinical notes and / or facility registries (medical records, discharge summaries)	TIMCI-09a								
	Diagnosis and care management recorded in CDSA	TIMCI-09b								
	Diagnosis and care management recorded by referral facility (medical records, discharge summaries)	TIMCI-09c								
Follow-up at Day 7		TIMCI-10								
Follow-up at Day 28		TIMCI-11								

¹ Data will be collected retrospectively for visits at facilities offering a higher level of care, including district hospitals, any study facility receiving referrals or admitting patients.²
If appropriate for clinical management.

³ Allocation at the level of the facility to intervention or control groups.

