8.3.3 Cost and cost-effectiveness study

When all the cost components have been collected, the data will be aggregated or collated in Excel. Once the summary is completed, a cost profile of the programme activities will be derived and after the total costs of the programme have been calculated, the unit costs will then be derived (i.e. total costs divided by the sample size). These profiles are useful in highlighting major cost components (and thus identifying potential areas where improvements in efficiency may have significant impact on costs). For this evaluation, analysis will focus on full costing and incremental costing approach. Total, average and incremental costs per year will be estimated. Costs associated with increasing the oxygen saturation referral threshold will be estimated based on the additional proportion of children meeting referral criteria.

When available, effectiveness data will be combined with the cost data and cost per DALY averted will be estimated. Effectiveness will be modelled using the information on severe outcomes such as mortality, and secondary hospitalization, adjusting as far as possible the level of severity of illness of the child at presentation.

At primary care facilities, these will include measurements (when taken by healthcare providers) such as anthropometry, respiratory rate, temperature and routine investigations where available (e.g. haemoglobin, CRP), and oxygen saturation (post-intervention/in intervention arms). We will also use diagnosis and severity classification recorded by primary care providers.

At hospital level, we will also utilize the same measurement data, and other vital sign data (such as a paediatric early warning score if recorded), decision to admit, intensive care and / or ventilation, provisional and final diagnosis, admission outcome (discharge, death, left against medical advice) and length of hospital stay. We will then use these indicators, along with mortality from phone call follow-up data by Day 28, to predict probability of mortality based on available literature. The DALY calculation will be based primarily on probability of mortality

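### The febrile denominator for malaria testing can differ by arm, because two of its three entry routes depend on what the provider measured or wrote down after allocation

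*SAP*

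**What the plan says.** SAP 6.1.4.1 gives three alternative routes to being febrile at Day 0. Two are in one clause: "history of fever was reported by the caregiver before the consultation or temperature was recorded to be above or equal 37.5" °C. The third is that "fever was recorded elsewhere in the registry (e.g. diagnosis" shows it. The next step is explicit: "Only febrile children will be counted in the denominator". SAP section 6 limits malaria outcomes to children aged 60 days or more.

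The sources differ in timing. Protocol Tab. 4 (section 6.5.1) has a form for "Clinical presentation and medical history reported by caregiver at baseline", completed by the research assistant. Physical measurements come from other forms, one for "Basic measurements and physical exams recorded in clinical notes and / or facility registries" and one for "Basic measurements and physical exams recorded in CDSA". Protocol 8.3.3, describing primary care data for the cost-effectiveness work, refers to "measurements (when taken by healthcare providers) such as anthropometry, respiratory rate, temperature", so a temperature is there only if someone took it.

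SAP 6.2.1 models other binary outcomes in the same way as the primary outcomes, with odds ratios and risk differences against control. SAP 6.1.4 discusses the different malaria testing strategies of the two countries but not dependence of the febrile group on arm. The sensitivity analyses in SAP 6.2.4 concern the primary outcomes only.

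**The concern.** A proportion compared between randomised arms is protected by randomisation only if its denominator is not itself shaped by the intervention. Here, a child with fever but no reported history enters the denominator if the provider measures or notes the fever, and drops out if not. Assessment behaviour is what the trial sets out to change: Protocol section 4 lists adherence to assessment guidelines among its objectives, and Protocol 6.3 has the CDSA steer the whole consultation.

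If one arm detects more such fevers, it adds children whom the other arm leaves out. A difference in the reported proportion could then reflect use of the thermometer rather than use of the malaria test, and a real gain in testing could be understated or reversed.

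**Working it through.** The documents give no fever prevalence, recording rate or testing rate, so there is no figure of the plan's to reproduce. Every value in steps 1 to 4 is an assumption, chosen to show the mechanism.

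**1. Formulas.** Let h be the share of children with caregiver-reported fever and t_h the share of these tested. Let m be the share with fever but no reported history, and r the share of m that the provider records. Let t_r and t_u be the testing rates in the recorded and unrecorded parts of m.

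- SAP rule: (h·t_h + m·r·t_r) / (h + m·r)
- All febrile children: (h·t_h + m·r·t_r + m·(1-r)·t_u) / (h + m)
- Caregiver-reported fever only: t_h
- All enrolled: h·t_h + m·r·t_r + m·(1-r)·t_u, plus any tests in afebrile children (taken as equal in both arms)

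**2. Example.** h = 0.50, t_h = 0.80, m = 0.10, t_r = 0.50, t_u = 0.05; r = 0.90 with CDSA and 0.30 in control.

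| Denominator | CDSA | Control | Difference (points) |
|---|---|---|---|
| SAP rule | 0.445/0.59 = 75.4% | 0.415/0.53 = 78.3% | -2.9 |
| All febrile | 0.4455/0.60 = 74.2% | 0.4185/0.60 = 69.8% | +4.5 |
| Caregiver-reported | 80% | 80% | 0 (by assumption) |
| All enrolled, before afebrile tests | 44.55% | 41.85% | +2.7 |

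A milder case (m = 0.05, t_h = 0.70, r = 0.70 v 0.50, other values unchanged) gives 0.3675/0.535 = 68.7% v 0.3625/0.525 = 69.0% by the SAP rule (-0.4). Among all febrile children it gives 0.36825/0.55 v 0.36375/0.55 (+0.8).

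**3. Direction.** The SAP proportion is a weighted average of t_h and t_r, and the weight on t_r grows with r. If the testing rates are equal across arms, the arm that records more looks worse when t_r < t_h, better when t_r > t_h, and the same when they are equal. A second set shows both signs: h = 0.60, t_h = 0.80, m = 0.05, t_u = 0.10, r = 0.80 v 0.20.

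- t_r = 0.40: 0.496/0.64 = 77.5% v 0.484/0.61 = 79.3% (-1.8), although all-febrile testing is 0.497/0.65 = 76.5% v 0.488/0.65 = 75.1% (+1.4).
- t_r = 0.95: 0.518/0.64 = 80.9% v 0.4895/0.61 = 80.2% (+0.7).

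Over h = 50-70%, m = 2-10% and t_r = 20-95%, with the same recording rates, the SAP-rule difference runs from -6.0 to +1.5 points.

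**4. If the CDSA also raises testing.** In the step 2 example, let the CDSA arm test 80% of recorded measured-only fevers instead of 50%. The SAP rule gives 0.472/0.59 = 80.0% v 78.3% (+1.7), against 0.4725/0.60 v 0.4185/0.60 (+9.0) among all febrile children. The sign is no longer reversed once that rate passes about 69%, from (0.783 × 0.59 - 0.40)/0.09. The gain is still understated.

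**5. Against sampling error.** Take 36,960 children per Tanzanian arm (Protocol summary) in 22 clusters, and the -1.8 point case. The control denominator is 0.61 × 36,960 = 22,546, about 1,025 per cluster. At the protocol's ICC of 0.001 the design effect is about 1 + 1,024 × 0.001 = 2.02, the standard error 0.54 points and the artefact 3.4 standard errors. At an assumed ICC of 0.05 the design effect is about 52, the standard error 2.8 points and the artefact 0.7 standard errors. It could look like a finding or be lost in noise.

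**The case against.** A reader might infer that the denominator does differ by arm and that the CDSA arm will look worse. The documents support neither. They hold no recording rates by arm, and steps 3 and 4 show that the sign is open. Protocol 6.3 allows malaria test recommendations in the algorithm where tests are routinely available, so testing of recorded fevers may rise together with recording.

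The scope is also narrower than the whole trial. The CDSA is used only in Tanzania. Pulse oximetry alone gives no direct reason to take a temperature, and every arm receives refresher training. SAP 6.1.4.1 does not say that temperatures held only in the CDSA count, although Protocol 8.1.1 links CDSA data to the research data. Caregiver report is itself one of the three routes, so only fever without a reported history is exposed.

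The strongest objection concerns the remedy. Restricting the denominator to caregiver-reported fever removes the artefact but shows 0 where the example in step 2 sets the true gain at +4.5 points. It also drops children with a recorded fever and no reported history, and may miss critical cases, who are seen before the interview (Protocol 6.5.1).

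All of this stands. It limits the claim to a possible bias of unknown sign and shows that caregiver report alone is not enough. It does not make the current comparison interpretable, because nothing in the SAP would let a reader separate a change in testing from a change in recording.

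**Conclusion.** The concern holds in a limited form. Two of the three routes into the febrile group arise after allocation, from provider behaviour that the intervention targets, and the SAP then compares the resulting proportion by arm with nothing to offset this. The denominator can differ by arm, chiefly for CDSA against control in Tanzania, and the bias can run either way. A few percentage points is a fair description of the size under the values tried, but that rests wholly on assumed fever, recording and testing rates. The outcome is neither primary nor secondary, and it lies outside the fallback procedure in SAP 4.1, so the trial's main conclusion does not depend on it.

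**What to change.** In SAP 6.1.4.1:

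1. Base the between-arm model on children aged 60 days or more whose caregiver reported fever before the consultation.
2. Add the proportion tested among all enrolled children aged 60 days or more. Its denominator does not depend on provider recording, so a gain among fevers found only on measurement is not lost (+2.7 points in the step 2 example).
3. Keep the three-source definition as a supporting result, with a table by arm of the children added by recorded temperature and by register entry. State whether temperatures held only in the CDSA count.

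SAP 4.2 sets a precedent: for adherence, it defines cough or difficulty breathing and IMCI classification by caregiver report and by provider diagnosis, and uses each separately.

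The cost is SAP wording, one more model and one table; the data are already collected. There are two downsides. Fever found only on measurement, and critical cases without a pre-consultation interview, leave the first comparison. The all-enrolled proportion is diluted by afebrile children, and would also move if testing of afebrile children changed. The two results should therefore be read together.
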